### 5.4. Endpoints

#### 5.4.1. *Efficacy Endpoints*

Migraine and headache endpoints are defined in [Table CGAN. 5.1](#). Each month is defined as a 30-day period with migraine or headache measures normalized from the visit intervals.

Table CGAN. 5.1 Migraine and Headache Endpoint Definitions

Diagnosis	Definition/Criteria
Migraine headache	A headache, with or without aura, of $\geq 30$ minutes duration with both of the following required features (A and B): A. At least 2 of the following headache characteristics: 
 
• Unilateral location
 
• Pulsatile quality
 
• Moderate or severe pain intensity
 
• Aggravation by or causing avoidance of routine physical activity
 
 AND B. During headache at least 1 of the following: 
 
• Nausea and/or vomiting
 
• Photophobia and phonophobia
 
 (Definition adapted from the IHS ICHD-3 beta)
Probable migraine headache	A headache missing 1 of the migraine features in the IHS ICHD-3 beta definition such that 1 feature in criteria A is missing or 1 feature in criteria B is missing; that is, meet at least 2 A criteria and none of the B criteria, or meet 1 of the A criteria and at least 1 of the B criteria.
Migraine headache day	A calendar day on which a migraine headache or probable migraine headache occurred.
Migraine headache attack	Beginning on any day a migraine headache and/or a probable migraine headache is recorded, and ends when a migraine-free day occurs.
Non-migraine headache	All headaches of at least 30 minutes duration not fulfilling the definition of migraine or probable migraine.
Non-migraine headache day	A calendar day on which a non-migraine headache occurred.
Headache day	A calendar day on which any type of headache occurs, (including migraine headache, probable migraine headache, and non-migraine headache).
Migraine headache days with abortive (acute) medication use	Calendar days on which migraine or probable migraine occurs, requiring abortive (acute) medication.
ICHD migraine headache day	A calendar day on which a migraine headache occurs.

Abbreviations: ICHD = International Classification of Headache Disorders; IHS = International Headache Society.

Headache information will be collected via an electronic patient reported outcome (ePRO) diary. Patients will need to enter diary data daily beginning from Visit 2, continuing until Visit 14.

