**Table CGAN. 5.2 ePRO Diary Questions, Responses, and Assignment to Headache Type**

QUESTION	RESPONSES	HEADACHE ASSIGNMENT
Q1. Yesterday, did you have a headache that lasted for thirty minutes or more?	Yes	Migraine if at least two migraine Criteria A's and at least one migraine Criteria B.
	No a	
Q2. Enter the total number of hours you had a headache yesterday.	Range 1 to 24	If $\geq 1$ , the headache will be counted as a headache day.
Q3. Yesterday, what was the worst headache pain?	Mild	
	Moderate	Migraine Criteria A
	Severe	Migraine Criteria A
Q4. Yesterday, was the headache throbbing or pounding?	Yes	Migraine Criteria A
	No	
Q5. Yesterday, was the headache just on the right or left side of your head?	Yes	Migraine Criteria A
	No	
Q6. Yesterday, was the headache made worse by your usual daily activity?	Yes	Migraine Criteria A
	No	
Q7. Yesterday, did the headache come with sensitivity to light and sound?	Yes	Migraine Criteria B
	No	
Q8. Yesterday, did you feel sick to the stomach or throw-up with the headache?	Yes	Migraine Criteria B
	No	
Q9. Yesterday, did you have your menstrual period (if female)?	Yes	
	No	
Q10. Yesterday, did you take any medicine for your headache?	Yes	Medication will only count as headache medication on a day a headache occurred.
	No	
Q11. Yesterday, did you take any medication for pain other than headache?	Yes	
	No	
Q12. Yesterday, did you experience aura?	Yes	
	No	
Q13. Yesterday, did you experience any warning symptoms other than aura (prodrome symptoms) that a migraine was coming?	Yes	
	No	

a If "No" is answered for Q1, then the patients will skip Q2 - Q6, only answer questions Q7 - Q13.

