**Primary Measure: the Number of Monthly Migraine Headache Days**

The primary measure is the number of monthly migraine headache days. A migraine headache day is defined as a calendar day on which a **migraine or probable migraine** occurs.

The primary measure of the number of monthly migraine headache days will be summarized from the daily ePRO data for each patient in that period (including 30 days of daily data from the baseline period prior to randomization, 6 months of daily data during the treatment phase, and 4 months of daily data during the post-treatment phase).

The daily data will be aggregated, and the number of migraine headache days will be provided for each of the 30-day periods. In calculating the number of migraine headache days for each period, if the period is not equal to 30 days, the number of migraine headache days will be normalized by multiplying the number of migraine headache days by  $(30/x)$  where 'x' is the total number of non-missing diary days in the period.

For the baseline period (Visit 2 to Visit 3), once a patient becomes eligible before Visit 3 judged from the daily ePRO data (this is called **eligible day**), then all ePRO data after the eligible day to Visit 3 will be ignored.

Example: A patient has Visit 2 = 2016/Jan/1. He records diary on Jan/2 for his headache information on Jan/1. He records diary everyday (no missing data.) He records diary on Jan/31 for his headache information on Jan/30 which ends up as 5th migraine headache day during the baseline period (starting from Jan/1.) He becomes eligible for CGAN study (assuming all other eligibility conditions are met.) He goes to a site on Feb/ 4 (Visit 3) and gets 1st injection on the day. In this case **eligible day** is 2016/Jan/30. All diary data of Jan/1, Jan/2,..., Jan/30 will be used as baseline period data. All diary data of Jan/31, Feb/1, Feb/2, Feb/3 will be ignored. Diary data on Feb/4 (Visit 3) is used for Month 1 period data.

For the double blind period (SP III), Month 1 period data is based on headache information from Visit 3 up to on Visit 5 – 1 day. Month 2 period data is based on headache information from Visit 5 up to Visit 6 – 1 day. Month 3, to Month 6 will be defined similarly.

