For the 4 months of the post-treatment period, the monthly interval will be derived as below. Firstly, the 2-month visit interval will be split into two one-month periods for efficacy measures. If the number of days between two visits (visit x + 1 date - visit x date + 1) is even, the first half will be in the first one-month period and the second half will be in the second one-month period. If the number of days between two visits is odd, then the days will be split similarly, but the first one-month period will have one day more than the second one-month period. Secondly, after the two-month visit intervals are split into two one-month periods, the monthly data will be derived in the same way for each one-month period as for treatment phase. For patients who discontinued early during the post-treatment phase, if the date of discontinuation is within 30 days of previous visit date, all data between the previous visit date and the discontinuation date will go to one monthly period; if the date of discontinuation is more than 30 days of the previous

visit date, then the first 30 days will be the first monthly period, and the rest will be considered as part of the second monthly period.

This approach to missing ePRO diary data assumes that the rate of migraine headaches per day is the same for days with missing and non-missing ePRO diary days, and it is missing at random (MAR). The same approach will also be applied to secondary and exploratory efficacy measures that are derived from ePRO data.

Example 1: A patient has 64 days between Visit 13 and Visit 14. He completes the study on Visit 14. Then he has

- 1st half month = ePRO diary data from day 1 to day 32
- 2nd half month = ePRO diary data from day 33 to day 64.

Example 2: A patient has 64 days between Visit 13 and Visit 14. He discontinues the study on Visit 14 (i.e., disposition is not marked as completed). Then he has

- 1st half month = ePRO diary data from day 1 to day 30
- 2nd half month = ePRO diary data from day 31 to day 64.

Example 3: A patient has 70 days between Visit 13 and Visit 14 (outside of visit allowance). He completes the study on Visit 14. Then all data will be captured and he has

- 1st half month = ePRO diary data from day 1 to day 35
- 2nd half month = ePRO diary data from day 36 to day 70.

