#### **5.5.7. Electronic Patient Reported Outcomes Diary Compliance**

Electronic patient reported outcomes diary compliance at each month period and for overall will be calculated:

- SP III: baseline, Month 1, ..., Month 6, overall (Month 1 through Month 6) for ITT population
- SP IV: Month 7, ..., Month 10, overall (Month 7 through Month 10) for post treatment population

Diary compliance at each period is calculated as:

$$\frac{\text{Actual number of diary days in the period}}{\text{Expected number of diary days in the period}} * 100$$

Expected number of Diary days for baseline is calculated as date when a patient becomes eligible day minus date of Visit 2+1 (diary for Visit 2, diary for Visit 2+1, ..., diary for eligible day).

For each patient, overall diary compliance for SP III is average of monthly compliance in SP III (Month 1, ..., Month 6). If he discontinues early, then ignore the rest of the month. In this case, the last month compliance is based on  $\max(30, \text{the total number of calendar days in that month})$  (See Section 5.4.1)

Expected number of Diary days for Month 7, Month 8, Month 9, and Month 10 in SP IV is calculated similarly. Note that 2-month visit interval (e.g. Month 7 and Month 8) will be split into two one-month interval as defined in Section 5.4.1. The section explains how to handle early discontinuation case.

For each patient, overall diary compliance for SP IV is average of monthly compliance in SP IV (Month 7, ..., Month 10). If he discontinues early, then ignore the rest of the month. In this case, the last month compliance is based on  $\max(30, \text{the total number of calendar days in that month})$  (See Section 5.4.1)

Example: Expected number of diary days in the period Month 3 = date of Visit 7 – date of Visit 6 (diary for Visit 6, diary for Visit 6+1 day, ..., diary for Visit 7-1 day.)

In addition following will be summarized for each month and for overall:

- subjects with  $\geq 80\%$  compliance
- subjects with  $\geq 50\%$  compliance

Treatment comparisons for diary compliance for each month and for overall will be performed separately using an ANOVA with treatment in the model.

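### The SAP's follow-up month rule counts both end visits, contrary to its treatment-phase rule; read literally, the Visit 13 day falls in Month 8 as well as Month 9 and Month 10 expects an unreportable Visit 14 day

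*SAP*

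**What the plan says.** For Study Period IV, SAP 5.4.1 (primary measure) takes each two-month visit interval and splits it in half. The interval's length carries a + 1: "If the number of days between two visits (visit x + 1 date - visit x date + 1) is even", the halves are equal; if the count is odd, "the first one-month period will have one day more than the second one-month period". Example 1, a completer with 64 days, uses every counted day: "2nd half month = ePRO diary data from day 33 to day 64". Example 3 does the same with 70 days (35/35).

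The same section defines treatment-phase months differently: "Month 2 period data is based on headache information from Visit 5 up to Visit 6 – 1 day". SAP 5.5.7 agrees with that version: "Expected number of diary days in the period Month 3 = date of Visit 7 – date of Visit 6". It says that expected days in Months 7 to 10 are obtained by analogy and refers back to the 5.4.1 split.

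Three other statements fix what the diary can hold:
- Each entry asks about the day before: "Q1. Yesterday, did you have a headache that lasted for thirty minutes or more" (SAP Table CGAN. 5.2).
- Data are dated by the headache day, not the entry day: "He records diary on Jan/2 for his headache information on Jan/1" (SAP 5.4.1).
- Entry stops at the last visit: "Patients will need to enter diary data daily beginning from Visit 2, continuing until Visit 14" (SAP 5.4.1). The patient is discharged there (Protocol 5.1, Study Period IV).

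**The concern.** A count with + 1 includes both end days. Two consecutive intervals counted that way share the visit between them. The interval from Visit 12 to Visit 13 ends on the Visit 13 day (Month 8), and the interval from Visit 13 to Visit 14 begins on it (Month 9). The last interval also ends on the Visit 14 day, whose headache data would be entered one day after discharge. Nothing in the SAP removes either day.

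The diary-based follow-up months feed these outputs (SAP Table CGAN. 5.5 and 5.5.7):
- the combined treatment and follow-up models for migraine headache days (MHD) and for MHD with acute medication;
- the combined 50%, 75% and 100% response models;
- time to first loss of 50% response;
- follow-up diary compliance.

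Two programmers working from the same text could build different months.

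**Working it through.** **Inputs.** Target spacing in follow-up is 60 and 60 days, each ± 5 (Protocol section 2). The count, split and diary rules are those set out above.

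**Reproducing the SAP's examples.** With n counted days, the first month has ceil(n/2) days and the second has the rest. n = 64 gives 32/32 (Example 1) and n = 70 gives 35/35 (Example 3). Both match, but they do not settle the calendar. Sixty-four days can be a date difference of 63 with Visit 14 as day 64, or a difference of 64 with Visit 14 minus 1 as day 64.

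Example 7 does discriminate. It has 14 days between Visits 5 and 6, with data on days 1 to 14. The treatment-phase rule yields as many days as the plain date difference, so the difference must be 14. A + 1 count of 14 would mean a difference of 13 and only 13 days of data. The SAP therefore uses the phrase for days between visits in two senses.

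**Enumerating the calendar.** Literal rule: n = date difference + 1, both ends included. Treatment-phase rule: n = date difference, closing visit excluded. The last reportable day is Visit 14 minus 1, so maximum Month 10 compliance under the literal rule is (days in Month 10 − 1) / (days in Month 10).

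| Gaps (days) | Literal Months 7–10 | Assigned / distinct days | Max. Month 10 compliance | Months 7–10 without + 1 |
|---|---|---|---|---|
| 55/55 | 28/28/28/28 | 112 / 111 | 27/28 = 96.4% | 28/27/28/27 |
| 60/60 | 31/30/31/30 | 122 / 121 | 29/30 = 96.7% | 30/30/30/30 |
| 61/60 | 31/31/31/30 | 123 / 122 | 29/30 = 96.7% | 31/30/30/30 |
| 63/63 | 32/32/32/32 | 128 / 127 | 31/32 = 96.9% | 32/31/32/31 |
| 65/65 | 33/33/33/33 | 132 / 131 | 32/33 = 97.0% | 33/32/33/32 |

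In every literal row Visit 13 lies in Months 8 and 9, and Visit 14 lies in Month 10. Without the + 1, Visit 13 is in Month 9 only, Visit 14 is in no month, and 100% compliance is attainable. Visit 12 is never duplicated, because Month 6 ends the day before it.

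**Effect on a Month 8 value.** At a 60-day gap, literal Month 8 is 29 days that belong there under either rule, plus Visit 13. Suppose those 29 days hold 4 MHD and the diary is complete.
- Visit 13 is an MHD: 5 × 30/30 = 5.00. On the 29 days alone: 4 × 30/29 = 4.14. Difference +0.86.
- Visit 13 is not an MHD: 4 × 30/30 = 4.00. Difference −0.14.
- At that patient's daily rate, 4/29 = 0.138, the expected difference is 0.138 × 0.862 − 0.862 × 0.138 = 0.

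Under the treatment-phase rule the thirtieth day is the one just before those 29, because the midpoint moves by a day. Month 8 is then 5.00 or 4.00 according to that day, again 4 + 0.138 = 4.14 on average.

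**Effect on response status.** With an assumed baseline of 9 MHD, 5.00 is a reduction of (9 − 5)/9 = 44%, while 4.14 is (9 − 4.14)/9 = 54%. This patient moves from responder to loss of response.

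**Effect of the Visit 14 day.** SAP 5.4.1 normalises by 30/x, with x the non-missing diary days. An unreported day is not in x, so the Month 10 rate does not change. Only compliance does. With 30 days expected, a completer needs 16 entries to exceed the 50% cut; with the unreportable day left out of the denominator, 15 of 29 would do.

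**The case against.** The strongest reply is that the overlap is inferred. The + 1 stands in a parenthesis whose job is to decide odd or even. The SAP never gives day 1 a calendar date, it says the split months are then handled by the treatment-phase method, and 5.5.7 extends its compliance rule by analogy. A sensible programmer might build non-overlapping months. That stands as far as practice goes, so the overlap should be called the literal reading, not a settled fact. It does not rescue the text. A 60-day gap would still be counted as 61, labelled odd and split 31/30, although the treatment-phase rule supplies only 60 days.

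A reader might also infer more than the documents support:
- **That Visit 13 is wrong in both months.** It belongs in Month 9 under any reading. Only its inclusion in Month 8 is wrong.
- **That follow-up migraine counts are inflated.** The day enters both numerator and denominator, and the expected shift at a constant daily rate is zero. The rule is also the same in every arm.
- **That many results change.** At an assumed 3.5 to 5 MHD per 30 days, Visit 13 is an MHD for about 12% to 17% of patients (3.5/30 to 5/30). That is not the frequency of changed results. Time to loss of response covers only Month 6 responders, and a change needs a patient within about a day of the threshold. The documents give no basis for estimating how often that occurs.
- **That Month 10 data are lost.** A ceiling near 97% is far above the 80% and 50% summary levels, and only a patient at the 50% boundary could be affected.

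The reach is limited as well. About 240 patients are expected to roll over and skip follow-up (Protocol 7.8.1), against an estimated 383 completers (SAP 5.2). The SAP's revision history itself calls the combined-period efficacy analyses less informative for that reason.

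**Conclusion.** The point holds as an internal inconsistency in a derivation rule. The follow-up count with + 1 cannot be reconciled with the treatment-phase months, the Month 3 expected-days example or Example 7. Read literally, it puts Visit 13 in Month 8 as well as Month 9 and caps Month 10 compliance at 96.4% to 97.0% across the spacings tried (96.7% at target).

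The size is one day per affected month, only in patients who enter Study Period IV. Individual Month 8 values and near-threshold responses can change; averages should not. The primary endpoint, the key secondary endpoints of the double-blind phase, alpha and power are not touched. The zero average shift assumes a constant daily rate within a patient. The response example assumes 4 MHD in 29 days and a baseline of 9.

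**What to change.** In SAP 5.4.1, define each Study Period IV interval as Visit x through the day before Visit x+1, with length equal to the visit x+1 date minus the visit x date (delete the + 1), and split that interval into the two months. In SAP 5.5.7, state that the same days are the expected diary days for Months 7 to 10.

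This costs one deletion and a clause in each section. Examples 1, 3 and 7 need no change, and Months 1 to 6 are unaffected. If follow-up datasets were already programmed, check which convention was used and rerun only the outputs listed above if it was the literal one.

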#### **Key/Other Secondary and Exploratory Efficacy Measures based on migraine headache and migraine acute treatment**

The same approach to adjusting the number of days within each period to a 30-day period and the same approach to imputing monthly data based on compliance as for the primary measure will be applied to all efficacy measures that are derived from ePRO diary data and need normalization to 30-day period, including:

- **Number of ICHD migraine headache days** is calculated as the number of calendar days in a 30-day period on which a migraine occurs. Probable migraine is excluded.
- **Number of headache days** is calculated as the number of calendar days in a 30-day period on which a headache occurs.
- **Number of moderate to severe headache days** is calculated as the number of calendar days in a 30-day period on which a headache occurs with a moderate or severe severity.
- **Number of headache hours** is calculated as the total number of headache hours in a 30-day period on days when a headache occurred.
- **Number of migraine headache hours** is calculated as the total number of headache hours in a 30-day period on days when a migraine or probable migraine occurs.

- **Number of migraine headache days with abortive (acute) medication use** is calculated as the number of calendar days in a 30-day period on which migraine or probable migraine occurs and abortive (acute) medication is used.
- **Number of migraine attacks per 30-day period** is calculated as the number of sets of consecutive days with migraine or probable migraine separated by at least one migraine-free day. For example, a migraine or probable migraine starting on 5 JAN and ending on 6 JAN will result in a migraine/probable migraine-free day on 7 JAN (assuming that there is no migraine/probable migraine on 7 JAN). This will count as one migraine attack that started on 5 JAN and ended on 6 JAN. For a migraine attack that begins in one 30-day period but ends in another, only one migraine attack will be counted in the first of the two periods. For example, in the case of 7 days of consecutive migraine/probable migraine headache with 3 days in the baseline period and 4 days in Month 1, only one migraine attack will be counted in the baseline period; the 4 days of migraine/probable headache in Month 1 will not be counted as a migraine attack in Month 1.

Additional secondary and exploratory efficacy measures will be derived as follows:

- **Mean severity of remaining migraine or probable migraine headaches on migraine headache days** will be calculated at each period (including baseline and any post-baseline periods). For the calculation of mean severity, for days with migraine or probable migraine, severity varies from 1 to 3 with 1 = mild, 2 = moderate, and 3 = severe. The mean severity for each period will be calculated as:

$$\frac{\text{Sum of Severity of migraine headache days in the period}}{\text{\# of migraine headache days in the period}}$$

For periods with zero migraine headache days, the mean severity is considered not applicable hence missing in the analysis data set.

- **Proportion of migraine headache days requiring medication use for abortive (acute) treatment** will be calculated at each period as:

$$\frac{\text{number of migraine headache days with abortive (acute) medication use}}{\text{number of migraine headache days in the period}}$$

For periods with zero migraine headache days, the proportion would be missing.

- **Percent change from baseline in the number of migraine headache days** (used for responder analysis) will be calculated for any post-baseline 30-day period as:

$$-1 * \frac{100 \times (\text{\# of MHD in Month Y} - \text{\# of MHD in baseline period})}{\text{\# of MHD in baseline period}}$$

An X% responder is defined as Yes, if any patient who has a  $\geq X\%$  reduction in the total number of migraine headache days in a 30-day period relative to baseline period, as No if otherwise. Therefore, if the percent change from baseline in the number of migraine headache days is  $\geq X\%$ , the patient will be counted as an X% responder. In other words, if the response rate defined above in a month is  $\geq X\%$ , then the patient will be an X% responder in that month. Indicators of X% responders will be derived for X=0, 5, 10, ..., 95, and 100.

- **50% responders sustained for at least three consecutive months to patient's endpoint in the double-blind treatment phase in the number of monthly migraine headache days** is defined as meeting 50% responder criteria in the number of migraine headache days for three consecutive months to patient's endpoint in the double-blind treatment phase. Anyone else are non-responders, including those discontinued early within 3 months and those continued after 3 months but do not meet 50% response criteria for their last three months.
- **50% responders sustained for all six months during treatment phase in the number of migraine headache days** is defined as meeting the 50% responder criteria in the number of migraine headache days for Months 1-6 in the double-blind treatment phase. Anyone else are non-responders, including those who discontinued early and those who completed 6-month treatment phase but did not meet 50% response criteria for one or more of the 6 months.
- **Time to first 50% response (in months)** is defined as the first month when 50% response is met during the double-blind treatment phase (SP III). If a patient has not met a 50% response during SP III, they will be censored at the last month where the 50% response status is not missing.
- **Time to first loss of 50% response in the post-treatment phase (in months)** is calculated for Month 6 50% responders as the time from the end of treatment phase to the first month in Study Period IV at which these patients no longer meet the 50% response criteria. Patients who continue meeting the criteria until the end of the study will be censored.
- **Time to initiation of treatment with a migraine preventive medication (in days) in the post-treatment phase** is defined as the date of start of the migraine preventive medication (based on information collected from concomitant medication electronic case report form [eCRF]) in the post-treatment follow-up phase (SP IV) minus the last visit date of SP III. If a patient did not initiate preventive treatment during SP IV, they will be censored at the disposition date of SP IV. This analysis will be conducted only for patients who entered SP IV.
- **Number of migraine headache days with photophobia and phonophobia** is calculated as the total number of migraine headache days with an answer of "yes" to Question 7 in a 30-day period.

- **Number of migraine headache days with nausea and/or vomiting** is calculated as the total number of migraine headache days with an answer of “yes” to Question 8 in a 30-day period.
- **Number of migraine headache days with aura** is calculated as the total number of migraine headache days with an answer of “yes” to Question 12 in a 30-day period.
- **Number of migraine headache days with prodromal symptoms other than aura** is calculated as the total number of migraine headached days with an answer of “yes” to Question 13 in a 30-day period.

**Other Efficacy Measures based on migraine headache and migraine acute treatment (not specified in Key/Other Secondary and Exploratory Efficacy Measures)**

- **Number of non-migraine headache days with aura** is calculated as the total number of non-migraine headache days with an answer of “yes” to Question 12 in a 30-day period.
- **Proportion of aura among migraine attacks** is calculated as follows: 1) among all the migraine attacks, only if aura happened on the first day of migraine attack, it will be counted as migraine attack with aura; 2) then within each period, the proportion of aura among migraine attack is calculated as the total number of migraine attacks with aura divided by the total number of migraine attacks. If the denominator is zero, then the proportion is set to missing.

Note: Some analysis listed below are based on combination medications. Combination medications (such as aspirin/acetaminophen/caffeine) will be counted in each medication category that applies (such as NSAIDs/aspirin and acetaminophen/paracetamol).

- **Number of days with abortive medication use** is calculated as the number of calendar days in a 30-day period on which an abortive medication is used.
- **Number of classes of abortive medications** is calculated as the total number of classes of abortive medications during a 30-day period.
- **Number of classes of abortive medications used on migraine headache days** is calculated as the total number of classes of abortive medications taken on migraine headache days during a 30-day period.
- **Average number of classes of abortive medication use per day** is calculated as follows for each monthly period:

$$\frac{\sum_{i=1}^5 i * n_i}{\sum_{i=0}^5 n_i}$$

Where  $n_i$  denotes the number of days during a monthly period with  $i$  class(es) of abortive medication use, and  $i = 0, 1, \dots, 5$ . Note that  $\sum_{i=0}^5 n_i = \#$  of non-missing (and complete) diary days for the period.

- **Average number of classes of abortive medications used per migraine headache day** is calculated as follows for each period:

$$\frac{\sum_{i=1}^5 i * m_i}{\sum_{i=0}^5 m_i}$$

Where  $m_i$  denotes the number of migraine headache days during a period with  $i$  class(es) of abortive medication use, and  $i = 0, 1, \dots, 5$ . If the denominator is zero (i.e., no MHD in the period), then the average is set to missing.

- **Number of days with triptans use** is calculated as the number of calendar days in a 30-day period on which triptan is used.
- **Number of migraine headache days with triptans use** is calculated as the number of migraine headache days in a 30-day period on which triptan is used.
- **Number of days with NSAIDs/aspirin use** is calculated as the number of calendar days in a 30-day period on which NSAIDs/Aspirin is used.
- **Number of migraine headache days with NSAIDs/aspirin use** is calculated as the number of migraine headache days in a 30-day period on which NSAIDs/aspirin is used.
- **Number of days with acetaminophen/paracetamol use** is calculated as the number of calendar days in a 30-day period on which Acetaminophen/paracetamol is used.
- **Number of migraine headache days with acetaminophen/paracetamol use** is calculated as the number of migraine headache days in a 30-day period on which acetaminophen/paracetamol is used.
- **Number of days with ergots use** is calculated as the number of calendar days in a 30-day period on which ergots are used.
- **Number of migraine headache days with ergots use** is calculated as the number of migraine headache days in a 30-day period on which ergots are used.
- **Number of days with anti-nausea use** is calculated as the number of calendar days in a 30-day period on which anti-nausea is used.
- **Number of migraine headache days with anti-nausea use** is calculated as the number of migraine headache days in a 30-day period on which anti-nausea is used.

- **Number of days with multiple class medication use** is calculated as the number of calendar days in a 30-day period on which multiple class medication is used. Multiple class medication use is defined as using at least two classes of the following 5 classes on a day: triptans, NSAIDs/aspirin, acetaminophen/paracetamol, ergots, anti-nausea.
- **Number of migraine headache days with multiple class medication use** is calculated as the number of migraine headache days in a 30-day period on which multiple class medication is used. Multiple class medication use is defined as using at least two classes of the following 5 classes on a day: triptans, NSAIDs/aspirin, acetaminophen/paracetamol, ergots, anti-nausea.
- **Number of migraine headache days with menstrual period** is calculated as the total number of migraine headache days with an answer of “yes” to Question 9 in a 30-day period. (Note: The analysis population is based on female who have at least one “Question 9 =Yes” through the entire study in CGAN.
- **Number of days with abortive medication use on non-headache days** is calculated as the number of calendar days in a 30-day period on which an abortive medication is used and “Question 1 = No”.

The following analysis is based on weekly data:

- **Number of weekly migraine headache days in Month 1** is calculated as the number of migraine headache days in a 7-day period on which a migraine headache occurs. At Month 1, the first 7 calendar days will be counted as week 1, the second 7 calendar days will be counted as week 2, the third 7 calendar days will be counted as week 3, the rest of the calendar days (up to Visit 5 – 1 day) will be counted as week 4. If diary is missing on a certain day, then it is counted as non MHD day. If patients discontinues early, then the rest of the days are considered non MHD day.

**Example:** Suppose duration of Visit 3 (2018/Jan/1) and Visit 5 (2018/Jan/31) is 30 days. Then duration of week 4 is 9 days with Jan/22, Jan/23, ..., Jan/30. Note that Jan/31 is counted for Month 2.

